## **8 METHODOLOGY/STUDY VISITS**

### **8.1 Screening Procedures: Visit 1 (Days -30 to -14)**

The Investigator will inform each prospective subject of the nature of the study, explain the potential risks, and obtain written informed consent from the subject prior to performing any study-related procedures.

Screening evaluations will consist of the following:

- Assessment of the disease status outlined in the inclusion/exclusion criteria
- Kt/V – the most recent value prior to Screening
- Date of birth, gender, and race
- Weight (pre-dialysis) and height
- Medical and surgical history
- Phosphate binder currently used and prescribed daily dose (must be three times a day)
- Physical examination
- Vital signs (pre-dialysis)
- Electrocardiogram evaluation
- Blood sample for clinical laboratory chemistry and hematology tests (pre-dialysis)
- FSH and pregnancy test, if applicable
- Concomitant medications

Subjects will be instructed not to take any other medications without the approval of the Investigator (except their existing phosphate binder medication). Results of the screening evaluations must meet the inclusion/exclusion criteria for the subject to be enrolled in the study.

## **8.2 Run-in Procedures: Visit 2 (Days -18 to -7) and Visit 3 (Days -9 to -2)**

- Serum phosphorus measurement (pre-dialysis)
- Concomitant medication
- AE assessments

## **8.3 Visit 4 (Day 1)**

- Inclusion/exclusion criteria (assess s-P criteria using the s-P measurement at Visit 3 and confirm other applicable inclusion/exclusion criteria)
- Vital signs (pre-dialysis)
- Serum phosphorus measurement (pre-dialysis)
- Blood collection for biomarker sample (pre-dialysis)
- Blood collection for FGF23 and PTH (pre-dialysis)
- Randomization

- Medical/surgical history (record only changes to medical history from Visit 1)
- Concomitant medications
- Study medication dispensing
- AE assessment

#### **8.4 Visits 5, 6, and 7 (Days 8, 15, and 22 ± 2 Days)**

- Serum phosphorus measurement (pre-dialysis)
- Study medication dispensing and/or return, if applicable
- Concomitant medications
- AE assessment

#### **8.5 Visit 8 (Day 29 ± 2 Days)**

- Weight (pre-dialysis)
- Vital signs (pre-dialysis)
- Blood collection for biomarker sample (pre-dialysis)
- Blood collection for FGF23 and PTH (pre-dialysis)
- Physical examination
- Electrocardiogram evaluation
- Blood sample for clinical laboratory chemistry and hematology tests (pre-dialysis)
- Blood sample for serum phosphorus (pre-dialysis)
- Pregnancy test (for women of child-bearing potential)
- Study medication return
- Concomitant medication
- AE assessment

#### **8.6 Early Termination Visit**

Evaluations scheduled for Visit 8 will be performed at the Early Termination visit for subjects who prematurely discontinue from the study.

### 8.7 Withdrawal Procedures

In the event of a subject's withdrawal, every effort will be made to complete the End-of-Study assessments (Visit 8). Withdrawn subjects will be followed until resolution of any AEs or until the unresolved AEs are judged by the Investigator to have stabilized.

### 8.8 Criteria for Study Termination

The study may be terminated at any time by the Sponsor if SAEs occur, or if, in the Sponsor's judgment, there are no further benefits to be achieved from the study, or for administrative reasons. A site may be closed out if the Investigator does not adhere to the protocol. In the event that the clinical development of the investigational product is discontinued, the Sponsor will inform all Investigators/institutions and the IRB overseeing the study.

### 8.9 Total Blood Volume Required for Study

The approximate blood volume required at scheduled visits for each subject is shown in the following table:

**Table 8-1: Approximate Blood Volume per Subject**

Test	No. of Samples	Volume Collected for Each Sample (mL)	Total (mL)
Chemistry + b-HCG+ FSH	2	7	14
Hematology (blood)	2	3	6
Phosphorus (serum)	8	4	32
PTH (plasma)	2	4	8
iFGF-23 (plasma)	2	4	8
cFGF-23 (plasma)	2	4	8
Serum biomarkers	2	5	10
Plasma biomarkers	2	6	12
Total	--	--	98

## **8.10 Protocol Deviations**

Subjects must fully meet the following criteria in order to be enrolled in the study. In keeping with regulatory requirements, if the Sponsor allows a subject to continue in the study following a protocol deviation, the deviation must be recorded as such.

A protocol deviation is defined as any intentional or unintentional change to, or noncompliance with, the approved protocol procedures or requirements. Deviations may result from the action or inaction of the subject, the Investigator, or site staff. Examples of deviations include, but are not limited to:

- Failure to adhere to study inclusion or exclusion criteria
- Failure to comply with dispensing or dosing requirements
- Use of medications, food, drink, herbal remedies, or supplements that are specifically prohibited in the protocol
- Missed or out-of-window visits
- Drug dosing not administered within the time frame specified in the protocol
- Failure to adhere to test requirements, including vital signs, laboratory tests, physical examination, medical history; either tests not done, incorrect tests done, or not done within the time frame specified in the protocol
- Procedural deviations such as incorrect storage of study medication, failure to update the informed consent form (ICF) when new risks become known, or failure to obtain IRB approvals for the protocol and ICF revisions

At the outset of the study, a process for defining and handling protocol deviations will be established. This will include determining which violations will be designated “critical”, requiring immediate notification to the Medical Monitor and the Sponsor. The Investigator is responsible for seeing that all known protocol deviations are recorded and handled as agreed.

## **9 STATISTICAL CONSIDERATIONS**

### **9.1 Statistical Analysis Plan**

A formal statistical analysis plan (SAP) will be provided separately. No changes are expected to the primary and secondary efficacy analyses. If the language in this protocol and the language in the SAP differ, the SAP governs. Results obtained from the analyses specified in the final approved version of the SAP will become the basis of the clinical study report for

this study. Any deviations from the final approved version of the SAP will be documented in the clinical study report.

## **9.2 Determination of Sample Size**

Approximately 214 ESRD subjects with hyperphosphatemia will be randomized in a 1:1 ratio to receive either tenapanor or placebo.

The primary endpoint is the change from baseline in s-P level at Week 4. Assuming a common standard deviation of 1.0 mg/dL, a sample size of 214 subjects (107 subjects/group) is expected to provide 95% power to detect a treatment difference of -0.5 mg/dL in the primary endpoint between the tenapanor and placebo groups. This calculation is based on a two-sample *t*-test with a significance level of 0.05 (two-sided) using SAS® PROC POWER. Under the same assumptions stated above, the sample size of 214 subjects will provide at least 85% power at the 0.01 significance level.

## **9.3 Analysis Populations**

The analysis populations defined for this study include: Intent-to-Treat (ITT) population, Full Analysis Set (FAS), Per-Protocol (PP) population, Week 4 Completers, and Safety population.

- Intent-to-Treat Population: will be comprised of all randomized subjects.
- Full Analysis Set: will include all ITT subjects who have at least one post-baseline s-P measurement during the study. It will be the population used for efficacy analyses to be performed with subjects as randomized.
- Per-Protocol Population: will be a subset of the FAS. It will be the analysis population for sensitivity analysis to be performed with subjects as randomized. Any subject who has a significant protocol deviation that could alter his/her efficacy outcome to treatment will be excluded from the PP population.
- Week 4 Completers: will be a subset of the FAS. It will include all FAS subjects who complete the s-P assessment at Week 4. It will be the analysis population for sensitivity analysis to be performed with subjects as randomized.
- Safety Population: will include all ITT subjects who receive at least one dose of the study medication (tenapanor or placebo). It will be the analysis population for safety analyses to be performed with subjects as treated.

## **9.4 Statistical Methods**

### **9.4.1 General Considerations**

All measures will be summarized descriptively by treatment (planned or actually received). Descriptive statistics including the number of observations (n), mean, standard deviation, median, minimum, and maximum will be presented for continuous variables. Summary statistics for iFGF23 and cFGF23 will also include geometric mean and geometric coefficient of variation %. Frequency (n) and percent (%) will be presented for categorical variables.

Individual subject data including relevant derived variables will be listed.

Analyses of efficacy endpoints will be performed on the FAS and the PP population. The statistical testing will be conducted at a significance level of 0.05 (two-sided) unless specified otherwise. Analyses of safety measures will be performed on the Safety population. No statistical testing will be conducted for safety measures.

All data manipulations, descriptive summaries, and statistical hypothesis testing will be performed using SAS®.

### **9.4.2 Baseline Descriptive Statistics**

Baseline characteristics, including demographics, disease characteristics, prior/concomitant medications, and medical/surgical history will be summarized by planned treatment.

### **9.4.3 Primary Efficacy Analysis**

The primary efficacy endpoint is the change from baseline in s-P level at Week 4. For this continuous endpoint, the following pair of hypotheses will be tested:

$$H_0: \mu_t = \mu_p$$

versus

$$H_1: \mu_t \neq \mu_p$$

where  $\mu_t$  and  $\mu_p$  denote the mean changes from baseline in s-P level at Week 4 in tenapanor and placebo groups, respectively. As the primary analysis, the treatment comparison of the mean change will be performed using a mixed-effects model for repeated measures (MMRM) on observed cases of the FAS. The MMRM will include type of phosphate binder (sevelamer or non-sevelamer), s-P level at Visit 3 (<7.5 mg/dL or  $\geq$ 7.5 mg/dL), treatment, visit (Week 1 through Week 4), treatment-by-visit interaction as fixed effects; baseline (Visit 4) s-P level and baseline-by-visit as covariates; and subject as a random effect. An unstructured (UN) covariance matrix will be used to model the within-subject errors. The least squares mean of

s-P changes within each treatment group will be reported. The difference in mean s-P changes at Week 4 between the tenapanor and placebo groups, along with the 95% confidence interval (CI), 99% CI, and *p*-value will also be reported.

The efficacy of tenapanor as an adjunctive therapy to phosphate binder therapy will be concluded if the estimated difference between the tenapanor and placebo groups in the mean s-P change from baseline at Week 4 is negative (i.e., <0) and the corresponding two-sided *p*-value  $\leq 0.05$ .

#### **9.4.4 Secondary Efficacy Analyses**

For binary response endpoints, the s-P response rate (i.e., the proportion of subjects achieving an s-P level <5.5 mg/dL) at each post-baseline visit will be estimated for each treatment group and be compared between the tenapanor and placebo groups with the 95% and 99% CIs. The *p* value will be obtained from the Cochran-Mantel-Haenszel test adjusting for type of phosphate binder (sevelamer or non-sevelamer) and s-P level at Visit 3 (<7.5 mg/dL or  $\geq 7.5$  mg/dL).

The relative change from baseline in iFGF23 (or cFGF23) at Week 4 will be analyzed using an analysis of variance (ANOVA) model with log-transformed relative change at Week 4 as the dependent variable. The model will include type of phosphate binder (sevelamer or non-sevelamer), s-P level at Visit 3 (<7.5 mg/dL or  $\geq 7.5$  mg/dL), and treatment as factors. Back-transformed point estimates and CIs (95% and 99%) will be reported.

Mean changes from baseline in s-P level at Week 1, Week 2, and Week 3 will be estimated for each treatment group and be compared between the tenapanor and placebo groups using the MMRM of the primary analysis.

The change from baseline in PTH at Week 4 will be analyzed using an analysis of covariance (ANCOVA) model with PTH change at Week 4 as the dependent variable. The model will include type of phosphate binder (sevelamer or non-sevelamer), s-P level at Visit 3 (<7.5 mg/dL or  $\geq 7.5$  mg/dL), treatment as factors and baseline PTH level as a covariate.

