**Efficacy Analyses:**

The primary efficacy endpoint is the change from baseline in s-P level at Week 4. For this continuous endpoint, the following pair of hypotheses will be tested:

$$H_0: \mu_t = \mu_p$$

versus

$$H_1: \mu_t \neq \mu_p$$

where  $\mu_t$  and  $\mu_p$  denote the mean changes from baseline in s-P level at Week 4 in the tenapanor and placebo groups, respectively. As the primary analysis, the treatment comparison of the mean change will be performed using a mixed-effects model for repeated measures (MMRM) on observed cases of the FAS. The MMRM will include type of phosphate binder (sevelamer or non-sevelamer), s-P level at Visit 3 (<7.5 mg/dL or  $\geq 7.5$  mg/dL), treatment, visit (Week 1 through Week 4), treatment-by-visit interaction as fixed effects; baseline (Visit 4) s-P level and baseline-by-visit as covariates; and subject as a random effect. An unstructured covariance matrix will be used to model the within-subject errors.

The MMRM approach will also be applied to the analysis of changes from baseline in s-P at Week 1, Week 2, and Week 3. An analysis of variance (or covariance) will be performed for iFGF23/cFGF23 (or PTH) endpoints.

For binary response endpoints, the response rate defined as the proportion of subjects reaching an s-P level <5.5 mg/dl will be estimated at each post-baseline visit and compared between treatment groups.

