## **7.5 Efficacy Endpoints**

Serum phosphorus levels will be measured at all study visits. The primary efficacy endpoint is the change from baseline in s-P level at Week 4. The efficacy of tenapanor as an adjunctive therapy to phosphate binder therapy will be evaluated based on the difference in mean change from baseline in s-P level at Week 4 between the tenapanor and placebo groups.

The following efficacy endpoints will be analyzed as key secondary endpoints:

- s-P response (achieving an s-P level <5.5 mg/dL) at Week 4
- Relative change from baseline in iFGF23 at Week 4, derived as (iFGF23 at Week 4/baseline iFGF23 – 1)
- Relative change from baseline in cFGF23 at Week 4, derived as (cFGF23 at Week 4/baseline cFGF23 – 1)

Other secondary endpoints to be analyzed include:

- Change from baseline in s-P level at Week 1, Week 2, and Week 3
- s-P response at Week 1, Week 2, and Week 3
- Change from baseline in PTH at Week 4

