#### **9.4.5 Multiple Comparisons / Multiplicity**

To control the overall Type I error rate associated with multiple comparisons on the primary and key secondary endpoints at the 0.05 level (two-sided), the following hierarchical testing strategy will be employed:

- A. Conduct the statistical testing for the primary comparison between the tenapanor and placebo groups on the primary endpoint “change from baseline in s-P level at Week 4” at the significance level of 0.05 (two-sided).
- B. If the result of the primary comparison on the primary endpoint is positive (i.e., estimated mean difference  $<0$  and  $p$ -value  $\leq 0.05$ ), then conduct the statistical testing for the primary comparison between the tenapanor and placebo groups on the key secondary endpoint “s-P response at Week 4” at the significance level of 0.05 (two-sided).
- C. If the result of the primary comparison on “s-P response at Week 4” is positive (i.e., estimated rate difference  $>0$  and  $p$ -value  $\leq 0.05$ ), then conduct the statistical testing for the following two key secondary endpoints using the Hochberg step-up procedure to control the family-wise Type I error rate at the significance level of 0.05 (two-sided):
  - Relative change from baseline in iFGF23 at Week 4
  - Relative change from baseline in cFGF23 at Week 4

Analyses of other secondary endpoints will be descriptive. No multiplicity adjustment will be made for these analyses.

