#### **9.4.7 Adjustments for Covariates**

In general, the two randomization stratification factors (type of phosphate binder and s-P level at Visit 3) will be adjusted in inferential analyses of efficacy endpoints. Detailed information on covariate adjustment is provided in [Sections 9.4.3](#) and [9.4.4](#).

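### The two alpha-controlled FGF23 endpoints are analysed without baseline FGF23 as a covariate, although it is measured at Visit 4 and the descriptive PTH endpoint is adjusted for its own baseline

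*Combined protocol and SAP*

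**What the plan says.** For both FGF23 markers, Section 9.4.4 states: "The relative change from baseline in iFGF23 (or cFGF23) at Week 4 will be analyzed using an analysis of variance (ANOVA) model". In full, this is an "analysis of variance (ANOVA) model with log-transformed relative change at Week 4 as the dependent variable". The factors are binder type, the Visit 3 serum phosphorus stratum and treatment. Section 7.5 defines relative change as the Week 4 value divided by baseline, minus 1, so baseline enters only as the denominator of the outcome.

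For PTH, the same section uses an ANCOVA with "treatment as factors and baseline PTH level as a covariate". The synopsis makes the same split: "An analysis of variance (or covariance) will be performed for iFGF23/cFGF23 (or PTH) endpoints". Section 9.4.7 adds no further covariate; it says that "the two randomization stratification factors (type of phosphate binder and s-P level at Visit 3) will be adjusted in inferential analyses of efficacy endpoints" and refers back to Sections 9.4.3 and 9.4.4. The primary MMRM in Section 9.4.3 includes baseline serum phosphorus and its interaction with visit.

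Section 9.4.5 places the FGF23 markers in step C, after the primary endpoint and the Week 4 response: "conduct the statistical testing for the following two key secondary endpoints using the Hochberg step-up procedure". PTH is among the other secondary endpoints, which are descriptive. Sections 1.3 and 8.3 schedule the baseline FGF23 and PTH blood together at Visit 4.

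**The concern.** The two FGF23 markers are the only continuous efficacy endpoints whose model leaves out their own baseline, yet they carry formal alpha, and no reason is given. A comparison of log ratios without a covariate forces the slope of log Week 4 on log baseline to be exactly 1. If the true slope differs, the residual variance is larger than it need be, and the estimate shifts with any chance imbalance in baseline FGF23. These endpoints are reached only after two gates and then share alpha, so precision that costs nothing is worth having.

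The sentence to be amended has a second defect. It log-transforms a quantity that Section 7.5 defines as a ratio minus 1. That is zero or negative for every subject whose FGF23 is unchanged or falls, and falling is the direction a treatment benefit would take.

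**Working it through.** **The plan's own figure.** Section 9.2 gives power for serum phosphorus only: 107 per group, difference 0.5 mg/dL, SD 1.0. The exact two-sample t-test gives 95.4% at two-sided 0.05 (stated 95%) and 85.4% at 0.01 (stated at least 85%), so both reproduce. No SD, effect or correlation is given for FGF23. Those are assumptions below.

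**Variance factor.** Let log baseline have SD 1, log Week 4 have SD k, and their within-subject correlation be rho.

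- Variance of the log ratio: 1 + k² − 2·rho·k
- Residual variance after adjusting for log baseline: k²(1 − rho²)
- The difference is (1 − rho·k)², which is never negative. Adjustment cannot lose precision beyond one degree of freedom, and gains nothing only when rho·k = 1.
- With k = 1 the factor is (1 − rho²)/(2 − 2·rho) = (1 + rho)/2. For rho = 0.5 this is 0.75, and the interval width is multiplied by √0.75 = 0.866.

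**Interval width and power, k = 1.** A standardised effect of 0.385 gives 80% power unadjusted with 107 per arm at two-sided 0.05 (210 df). Dividing it by the square root of the factor and using 209 df gives:

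| rho | Variance factor | CI narrower by | Power, from 80% | Equivalent unadjusted N (214/factor) |
|---|---|---|---|---|
| 0.5 | 0.75 | 13.4% | 89.9% | 285 |
| 0.7 | 0.85 | 7.8% | 86.0% | 252 |
| 0.8 | 0.90 | 5.1% | 84.0% | 238 |
| 0.9 | 0.95 | 2.5% | 82.0% | 225 |
| 0.95 | 0.975 | 1.3% | 81.0% | 219 |

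**Unequal SDs.** For k from 0.8 to 1.2 and rho from 0.5 to 0.95 the factor runs from 0.52 (k = 0.8, rho = 0.95: 0.0624/0.12) to 1.00. For example, k = 1.2 and rho = 0.8 give 0.5184/0.52 = 0.997.

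**Hochberg step.** In simulation (4,000 trials of 214, markers correlated 0.7, both gates passed), the chance of claiming iFGF23 rises from 76–78% to 88%, 84%, 81% and 79% for rho = 0.5, 0.7, 0.8 and 0.9. At 0.95 any gain is within simulation error.

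**Validity.** Simulated type I error per test, with normal and heavy-tailed data, is 4.6–5.2% with the covariate and 4.6–4.9% without (Monte Carlo SE 0.3 points). Neither model is biased on average.

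**Chance imbalance.** With a log-baseline SD of 1.0, a one-SE imbalance is √(2/107) = 0.137. The unadjusted log-ratio estimate moves by (1 − rho) × 0.137 in size: 0.068, 0.041 and 0.014 for rho = 0.5, 0.7 and 0.9.

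**Literal dependent variable.** The share of subjects with no defined log(ratio − 1) is P(ratio ≤ 1) = Φ(−ln(GMR)/SD), where GMR is the geometric mean ratio and SD that of the log ratio. With no change (GMR 1) it is 50%. With GMR 0.8 it is Φ(0.223/0.8) = 61% and Φ(0.223/0.4) = 71%. FGF23 is scheduled only at Visit 4 and Visit 8 or early termination, so if the LOCF rule in Section 9.4.6 carries baseline forward, the ratio minus 1 is exactly zero and again has no log.

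**The case against.** The strongest reply is that this is a prespecified, internally consistent choice and a valid test. Baseline is already in every outcome as the denominator, and PTH is analysed as an absolute change, so a different model for PTH is not in itself a contradiction. That stands: the point is efficiency and not validity, and what is missing is baseline as a covariate.

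The benefit also depends wholly on assumed values. It is small at rho of 0.9 or more with equal SDs, and negligible wherever rho·k is near 1. The 80% starting power is a convenience, the Hochberg figures are conditional on passing both gates, and all 214 subjects are counted although some missing data are expected. These limits affect the size of the gain and not its direction.

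The geometric summaries in Section 9.4.1 and the back-transformation in Section 9.4.4 suggest that the log ratio is intended. That is very likely, but a formally tested endpoint should say so.

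Finally, Section 9.1 lets a separate SAP govern, and its text is not among the documents supplied, so the point applies to the protocol wording. The same section expects no change to the secondary analyses, so a silent correction there cannot be presumed.

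**Conclusion.** The concern holds. The FGF23 models omit a prognostic covariate that the trial already measures and that the plan's other continuous efficacy models include. The cost is avoidable imprecision and sensitivity to chance baseline imbalance, with no type I error inflation and no average bias. If the log-scale SDs are equal and rho is 0.5 to 0.7, the gain is moderate: intervals 13.4% to 7.8% narrower and roughly 10 to 6 points of power from a base of 80%. At rho of 0.9 or above it is 1 to 2 points. The correlation, the SD ratio and the base power are all assumed. The undefined log is a defect of specification in the same sentence and should be settled with it. The change should be made, but the trial's conclusions do not depend on it.

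**What to change.** In Section 9.4.4, for iFGF23 and cFGF23:

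- State the dependent variable as log(Week 4/baseline), that is, the ratio and not the ratio minus 1.
- Analyse it by ANCOVA with binder type, Visit 3 serum phosphorus stratum and treatment as factors and the marker's own log baseline as covariate.
- Back-transform to a geometric mean ratio, and subtract 1 only when reporting relative change.

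Align the synopsis line and the SAP text, and fix the wording before unblinding. Leave the primary MMRM, the Cochran-Mantel-Haenszel response test and the testing order as they are. The cost is two sentences plus the matching text and one degree of freedom per model, with no added samples or subjects.

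### The model outcome for both FGF23 key secondary endpoints is the log of (Week 4/baseline − 1), which does not exist for any subject whose FGF23 falls or stays the same

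*Combined protocol and SAP*

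**What the plan says.** Section 7.5 lists relative change in iFGF23 and in cFGF23 at Week 4 as key secondary endpoints. The first is "derived as (iFGF23 at Week 4/baseline iFGF23 – 1" and the second "derived as (cFGF23 at Week 4/baseline cFGF23 – 1" (closing bracket omitted in both). Section 9.4.4 analyses each "using an analysis of variance (ANOVA) model with log-transformed relative change at Week 4 as the dependent variable", with the two stratification factors and treatment in the model, and promises back-transformed estimates with 95% and 99% CIs.

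On the population, Section 9.3 says of the FAS: "It will be the population used for efficacy analyses to be performed with subjects as randomized". Section 9.4.1 adds: "Analyses of efficacy endpoints will be performed on the FAS and the PP population". Section 9.4.5 tests the two FGF23 endpoints by the Hochberg procedure at two-sided 0.05, as step C of the hierarchy.

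The synopsis (Section 1.2) is no more specific: "An analysis of variance (or covariance) will be performed for iFGF23/cFGF23 (or PTH) endpoints". On the SAP, Section 9.1 says both "No changes are expected to the primary and secondary efficacy analyses" and "If the language in this protocol and the language in the SAP differ, the SAP governs".

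**The concern.** Sections 7.5 and 9.4.4, read together, make the dependent variable log(Week 4/baseline − 1). It has a value only for subjects whose FGF23 rose. No offset, floor or exclusion rule is given. The LOCF rule in Section 9.4.6 covers missing values, not undefined ones.

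Unless the SAP already corrects this, one of two things happens.

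- **The model is run as written.** Software drops the undefined values, so the analysis keeps a subset selected on the post-randomisation outcome. If tenapanor lowers FGF23, more tenapanor than placebo subjects are lost. This is no longer the FAS as randomised.
- **The problem is noticed at programming, and a transform is chosen then.** This is the likelier course. Plausible repairs can disagree on significance, and alpha is exposed if the choice is made after unblinding.

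Both endpoints carry confirmatory claims, so their outcome should be computable and fixed in advance.

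**Working it through.** **The plan's own figure.** The only design calculation is for the primary endpoint (Section 9.2): 107 per group, difference 0.5 mg/dL, SD 1.0 mg/dL. The noncentral t gives 95.4% power at 0.05 and 85.4% at 0.01, so both stated figures reproduce. They do not bear on FGF23, for which the protocol gives no power, spread or expected effect.

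**The algebra.** Let R = Week 4/baseline. The outcome as written is log(R − 1).

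| R | R − 1 | log(R − 1) | log(R) |
|---|---|---|---|
| 0.5 | −0.5 | undefined | −0.693 |
| 0.8 | −0.2 | undefined | −0.223 |
| 1.0 | 0 | undefined | 0 |
| 1.1 | 0.1 | −2.303 | 0.095 |
| 1.5 | 0.5 | −0.693 | 0.405 |
| 2.0 | 1.0 | 0 | 0.693 |

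If these were six subjects, the written model would use three: (−2.303 − 0.693 + 0)/3 = −0.999, and exp(−0.999) = 0.37, a 37% rise. All six on log(R) give 0.277/6 = 0.046, and exp(0.046) − 1 = 0.047, a 5% rise. Since exp() is always positive, the written model can only ever report an increase within an arm.

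**LOCF.** Section 1.3 schedules FGF23 only at Visit 4 and at Visit 8 or early termination. If LOCF carries baseline forward, R = 1 and the outcome is again undefined; log(R) would be 0.

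**Size.** These assumptions are not from the protocol: R is lognormal with log-SD 0.3, 0.5 or 0.8; 100 subjects per arm; true tenapanor/placebo ratio of geometric means 0.80; two-sided 0.05; two balanced binary factors with no effect.

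The share undefined in an arm is Φ(−log(GMR)/SD), where GMR is that arm's geometric mean of R. For GMR 0.8 and SD 0.3 this is Φ(0.223/0.3) = 0.77. The table shows that share for the tenapanor arm and single-endpoint power over 4000 simulated trials per setting. As written means the model on log(R − 1) among subjects with R > 1. Triples are for log-SD 0.3 / 0.5 / 0.8.

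| GMR placebo / tenapanor | Undefined, tenapanor | Power as written | Power with log(R) |
|---|---|---|---|
| 0.8 / 0.64 | 93 / 81 / 71% | 10 / 9 / 8% | >99 / 88 / 50% |
| 1.0 / 0.8 | 77 / 67 / 61% | 26 / 16 / 9% | >99 / 87 / 49% |
| 1.25 / 1.0 | 50 / 50 / 50% | 66 / 27 / 13% | >99 / 87 / 49% |
| 1.5 / 1.2 | 27 / 36 / 41% | 91 / 39 / 15% | >99 / 88 / 50% |

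Other results, in the same SD order:

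- **Hochberg pair, at least one rejection (endpoint correlation 0.3 to 0.8).** At 1.0/0.8: 34–35 / 18–21 / 11–12% as written, against >99 / 89–95 / 50–58% with log(R). At 1.5/1.2: 95–98 / 46–50 / 17–19%, against >99 / 89–95 / 51–58%.
- **Within-arm estimate, tenapanor.** At GMR 0.8, the truth is −20% and the written model reports +12 / +26 / +51%. At GMR 1.2, the truth is +20% and it reports +27 / +42 / +72%.
- **Between-arm ratio, truth 0.80.** At 1.0/0.8 the written model averages 0.66 / 0.76 / 0.83 and favours tenapanor in 91 / 82 / 74% of trials. At 1.5/1.2 it averages 0.58 / 0.71 / 0.80 and favours tenapanor in >99 / 96 / 82%.
- **Identical arms.** The written model rejects in 4.3–5.8% (one endpoint) and 4.3–5.2% (Hochberg pair).
- **Late choice among three repairs.** With rc = R − 1, the repairs are log(rc + 1), log(rc − minimum + 0.01) and log(max(rc, 0.01)). At 1.0/0.8 they disagree on significance in 1 / 18 / 23% of trials. With identical arms, taking the most favourable after unblinding rejects in 7.7–8.8%; each repair fixed in advance rejects in 4.6–5.4%.

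**The case against.** The strongest reply is that this is a drafting slip whose intent is clear. Section 9.4.1 adds geometric means and geometric CVs for FGF23, and Section 9.4.4 back-transforms; both fit the log of the ratio and neither fits the log of the ratio minus 1. A separate SAP governs and may already say so. A log that fails in a large share of subjects would hardly escape a programmer, so the power table describes the less likely branch.

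The late-choice figures also depend on the repairs compared. At 1.0/0.8, log ratio and floor disagree in about 1 / 15 / 18% of trials, but log ratio and shift in only about 0.1 / 4 / 5%. At 1.5/1.2 the three disagree less, about 0.2 / 11 / 18%. Neither the floor nor the shift is in the protocol. Every FGF23 input is assumed. Only two endpoints are touched, and only after steps A and B succeed.

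Most of this stands as a limit on the size. It does not remove the defect. Section 7.5 prints the minus 1 for both endpoints, Section 9.4.4 logs that defined quantity, and an intention inferred by the reader is not prespecification. The SAP may correct the variable, but Section 9.1 expects no change to these analyses, so a correction cannot be assumed.

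**Conclusion.** The concern holds, and the rule is wrong as written. The stated outcome cannot be computed for any subject whose FGF23 falls or is unchanged; this is exact and needs no distributional assumption. It affects two alpha-controlled endpoints and should be corrected before unblinding.

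The practical loss rests on the assumed lognormal ratio. Run as written, power falls slightly when FGF23 rises in most subjects with little spread (91% against >99%) and heavily otherwise (26% against >99% at GMR 1.0/0.8, SD 0.3). Within-arm estimates have the wrong sign for an arm whose FGF23 truly falls. The between-arm contrast points the right way on average but is not the ratio of geometric means. Type I error is at risk only if the repair is chosen after unblinding, where 7.7–8.8% is a worst case for the three repairs examined. The primary endpoint, s-P response, PTH and safety analyses are not affected. Whether the error reaches the governing SAP could not be checked.

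**What to change.** In Section 9.4.4, define the dependent variable for each FGF23 endpoint as log(Week 4/baseline), which equals log(relative change + 1). Report exp(LS mean) − 1 as the relative change within each arm and exp(difference in LS means) as the between-arm ratio of geometric means, each with its 95% and 99% CI. Section 7.5 can stay as the reporting scale. Confirm before unblinding that the SAP names the same variable.

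The cost is one sentence in the protocol and its match in the SAP. No new data, visits or sample size change are needed.
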